In the literature, several subsets of patients with lumbar degenerative disease who may profit more than others from lumbar spinal fusion have been identified.^{5,10} Accurate preoperative identification of patients at high risk for unsatisfactory outcome and vice-versa would be clinically advantageous, as it would allow enhanced resource preparation, better surgical decision-making, enhanced patient education and informed consent, and potentially even modification of certain risk factors for unsatisfactory outcome.¹¹ However, it is often impossible for clinicians to balance the many described single risk factors for each adverse event to arrive at a personalized risk-benefit profile in individual patients.

Machine learning (ML) methods have been extraordinarily effective at integrating many clinical patient variables into one holistic risk prediction tailored to each patient. One multicenter model based on classic statistics has already been described by Khor et al.¹² – However, upon external validation, it proved to be unreliable and rather poorly calibrated.¹⁰ Also, this model was based on a relatively small number of patients for ML. The aim of the FUSE-ML study is to develop and externally validate a robust ML-based prediction tool based on multicenter data from a range of

international centers that will provide individualized risk-benefit profiles tailored to each patient undergoing lumbar spinal fusion for degenerative disease.

Methods

Overview

Data will be collected by a range of international centers. Overall, the models will be built and publication will be compiled according to the transparent reporting of a multivariable prediction model for individual prognosis or diagnosis (TRIPOD) guidelines.¹³ One model will be created for each of the relevant outcomes detailed below.

University of Zurich ([name], [name]) is the sponsor of this study.

Ethical Considerations

Each center will be responsible for their own ethics board / institutional review board (IRB) approval and for establishing a data transfer agreement (DTA). The sponsor (University of Zurich) will present a standard DTA upon request. They must gain approval for retrospective or prospective data collection and sharing of the completely deidentified data with the sponsor. The sponsor can aid by providing this detailed study protocol. All study procedures will be carried out according to the Declaration of Helsinki and its amendments.

Inclusion and Exclusion Criteria

Patients with the following indications for thoracolumbar pedicle screw placement are considered for inclusion: Degenerative pathologies (one or multiple of the following: spinal stenosis, spondylolisthesis, degenerative disc disease, recurrent disc herniation, failed back surgery syndrome (FBSS), radiculopathy, pseudarthrosis). Patients undergoing surgery for – as the primary indication – infections, vertebral tumors, as well as traumatic and osteoporotic fractures or deformity surgery for scoliosis or kyphosis are not eligible. Patients with moderate or severe scoliosis (Coronal Cobb's >30 degrees / Schwab classification sagittal modifier + or++) are not eligible. Patients undergoing surgery at more than 6 vertebral levels are also not eligible. Patients with missing endpoint data at 12 months will be excluded. Patients are required to give informed consent. Only patients aged 18 or older are considered for inclusion.

Data Collection

Each center will collect their data either retrospectively, from a prospective registry, or from a prospective registry supplemented by retrospectively collected variables. Each center has to contribute a minimum of 100 patients with complete 12-month follow-up data to be included in the study. A standardized Excel database will be provided by the sponsor for anonymous data entry. The data will be entered in standardized and deidentified form. This Excel database will only contain a study-specific patient number. Each center will keep an internal spreadsheet in which the study-specific patient numbers can be traced back to center-specific patient-numbers, should this be necessary. The deadline for submission of the complete data to the sponsor institution is **13th of August 2021**.

Authorship

Centers will have to contribute at least 100 cases with complete outcome data in total to be included in the study. Each participating center will be able to designate a maximum of four authors to be included in the author list. Any other center-specific contributors will be listed as full members of the FUSE-ML study group and will be granted full PubMed / Medline contributor status. The sponsor institution will have six primary author positions available.

Primary Endpoint Definitions

Several endpoints will be assessed:

- **1. Oswestry Disability Index (ODI) at 12 months.**
- **2. Visual Analogue Scale (VAS-BP, 0 to 100) for back pain at 12 months.** *This can also be a converted numeric rating scale (NRS) from 0-10, or a VAS from 0 to 10 converted to 0 to 100.*
- **3. Visual Analogue Scale (VAS-LP, 0 to 100) for leg pain at 12 months.** *This can also be a converted numeric rating scale (NRS) from 0-10, or a VAS from 0 to 10 converted to 0 to 100.*

These outcomes will be dichotomized using the minimum clinically important difference (MCID) according to Ostelo et al.¹⁴ Thus, a 30% or greater improvement in a specific score compared to baseline will be considered as achievement of MCID (clinical success) in that specific score. If patients presented with zero symptoms initially (in either ODI, NRS-BP or NRS-LP), and remained at zero for that score, this will also be defined as MCID for that score.

Features and Their Definitions

All features are measured or estimated preoperatively. In addition to the endpoints, the following input features will be collected:

- Age (years)
- Gender (m/f)
- Presence of the following indications for surgery (choose all that apply):
 - Spondylolisthesis
 - (Recurrent) disc herniation
 - Radiculopathy
 - Chronic low back pain (CLBP) / Degenerative disc disease (DDD)
 - Failed back surgery syndrome (FBSS)
 - Lumbar spinal stenosis
 - Pseudarthrosis
- Index Level(s) (choose all that apply, T12 – S1)
- Height (cm)

- Weight (kg)
- BMI (kg/m²)
- Smoking status (active / ceased / never)
- Preoperative (baseline) ODI
- Preoperative (baseline) VAS-BP
- Preoperative (baseline) VAS-LP
- American Society of Anesthesiologists (ASA) Score (1-2 / 3 or higher)
- Preoperative use of opioid pain medication (yes / no)
- Asthma pulmonale as a comorbidity (yes / no)
- Prior thoracolumbar spine surgery (yes / no)
- Race/Ethnicity (Caucasian / Black / Asian / Other)
- Surgical approach (choose all that apply: TLIF / PLIF / ALIF / Lateral)
- Pedicle screw insertion (yes / no)
- Minimally invasive technique (yes / no)

Sample Size

While even the largest cohort with millions of patients is not guaranteed to result in a robust clinical prediction model if no relevant input variables are included (“garbage in, garbage out” – do not expect to predict the future from age, gender, and body mass index), the relationship among predictive performance and sample size is certainly directly proportional, especially for some data-hungry ML algorithms. To ensure generalizability of the clinical prediction model, the sample size should be both representative enough of the patient population, and should take the complexity of the algorithm into account. For instance, a deep neural network – as an example of a highly complex model – will often require thousands of patients to converge, while a logistic regression model may achieve stable results with only a few hundreds of patients. In addition, the number of input variables plays a role. Roughly, it can be said that a bare minimum of 10 positive cases are required per included input variable to model the relationships. Often, erratic behavior of the models and high variance in performance among splits is observed when sample sizes are smaller than calculated with this rule of thumb. Of central importance is also the proportion of patients who experience the outcome. For very rare events, a much larger total sample size is consequentially needed. For instance, a prediction based on 10 input features for an outcome occurring in only 10% of cases would require at least 1000 patients including at least 100 who experienced the outcome, according to the above rule of thumb. In general and from personal experience, we do not recommend developing ML models on cohorts with less than 100 positive cases and reasonably more cases in total, regardless of the rarity of the outcome. Also, one might consider the available literature on risk factors for the outcome of interest: If epidemiological studies find only weak associations with the outcome, it is likely that one will require more patients to arrive at a model with good predictive performance, as opposed to an outcome which has several highly associated risk factors, which may be easier to predict. Larger sample sizes also allow for more generous evaluation through a larger amount of patient data dedicated to training or validation, and usually results in better calibration measures.

Between 20% and 40% of patients report no clinically relevant improvement after spinal fusion (minority class).^{5,10,12,15} For sample size calculation, we take 20% for a conservative estimate. Consequently, for this study, based on our expertise and on the rules of thumb mentioned above, we estimate that a minimum of 200 patients with a negative outcome (minority class) are required to extract generalizable feature relationships. With an estimated incidence of approximately 20% as explained above, that means that a minimum of around **1000 patients are required for training. For adequate evaluation of calibration at external validation, we estimate that another 300 patients will be required** (thus, approximately 60 patients with a positive outcome). Thus, in total, we estimate that **a minimum of 1300 patients** are necessary to arrive at a robust model. More data will likely lead to greater performance and better calibration.

Predictive Modeling

A KNN imputer will be co-trained to impute any missing data that may occur in future application of the model. If there is missing data in the training set, it will be imputed using said KNN imputer.¹⁶ Features or patients with a missingness greater than 25% will be excluded. Data will be standardized and one-hot-encoded. In case of major class imbalance – which is expected for the abovementioned endpoint – random upsampling or synthetic minority oversampling (SMOTE) will be applied to the training set.^{17,18} All features will initially be provided to the model for training. If necessary, we will apply recursive feature elimination (RFE) to select input features on the training data.¹⁹

We will trial the following algorithms for binary classification: Generalized linear model (GLM), generalized additive model (GAM), stochastic gradient boosting machine (GBM), naïve Bayes classifier, simple artificial neural network, support vector machine (SVM), and random forest. Each model will be fully trained and hyperparameter tuned where applicable. The final model will be selected based upon AUC, sensitivity, and specificity, as well as calibration metrics on the resampled training performance. Training will occur in repeated 5-fold cross-validation with 10 repeats.

The one final model will then be assessed on the external validation data only once. 95% confidence intervals for external validation metrics will be derived using the bootstrap.

The threshold for binary classification will either be identified on the training data alone using the AUC-based “closest-to-(0,1)-criterion” or Youden’s index to optimize both sensitivity and specificity, or will be optimized on the training set based on clinical significance (rule-out model). All analyses will be carried out in R Version 4.0.2 or more recent.²⁰

Evaluation

The performance of classification models can roughly be judged along two dimensions: Model discrimination and calibration.[46] The term *discrimination* denotes the ability of a prediction model to correctly classify whether a certain patient is going to or is not going to experience a certain outcome. Thus, discrimination described the accuracy of a binary prediction – yes or no. *Calibration*, however, describes the degree to which a model’s predicted probabilities (ranging from 0% to 100%) correspond to the actually observed incidence of the binary endpoint (true posterior). Many publications do not report calibration metrics, although these are of central importance, as a well-

calibrated predicted probability (e.g. your predicted probability of experiencing a complication is 18%) is often much more valuable to clinicians – and patients! – than a binary prediction (e.g. you are likely not going to experience a complication).²¹

Resampled training performance as well as performance on the external validation set will be assessed for discrimination and calibration.^{21,22} In terms of discrimination, we will evaluate AUC, accuracy, sensitivity, specificity, positive predictive value (PPV), negative predictive value (NPV), and F1 Score. In terms of calibration, we will assess the Brier score, expected-observed (E/O)-ratio, calibration slope and intercept, the Hosmer-Lemeshow goodness-of-fit test, as well as visual inspection of calibration plots for both datasets, which will also be included in the publication.

Interpretability

The degree and choice of methods for interpretability will depend on the finally chosen algorithm. Some algorithms can natively provide explanations as to which factors influence the outcome in what way. Thus, in case e.g. a GLM, GAM, or naïve Bayes classifier is chosen, the parameters / partial dependence values will be provided. For simple decision trees, diagrams of the decision-making process can be provided. Other models with higher degrees of complexity, such as neural networks or stochastic gradient boosting machines cannot natively provide such explanations. In that case, we will provide both AUC-based variable importance as well as model-agnostic local interpretations of variable importance using the LIME principle.^{23,24}

Expected Results

We expect to arrive at a generalizable model based on multicenter international data that is likely to predict consistently with an AUC of at least 0.70 and that is well-calibrated. A web-based prediction tool will also be created for each of the two models using the *shiny*²⁵ environment, much akin to e.g. <https://neurosurgery.shinyapps.io/impairment> (Also see for example: Staartjes et al., Journal of Neurosurgery, 2020²⁶). This web-based app will be available for free on any internet-capable device (mobile or desktop), and should be stable on most devices due to the server-based computing. The costs for maintaining the server will be carried by the sponsor. The collected data will be stored by the sponsor for 10 years. The large dataset will be open to further analysis and will be provided to any of the contributing centers at reasonable request and after approval by all other centers. The goal is to enable other analyses using the collected dataset. If any additional analyses lead to publication, all contributors will be included as co-authors and all co-authors will have the opportunity to review said manuscript beforehand. Any contributing study center has the right to veto publication of any subsequent analyses containing their own data.

References

1. Lambeek LC, van Tulder MW, Swinkels ICS, Koppes LLJ, Anema JR, van Mechelen W. The trend in total cost of back pain in The Netherlands in the period 2002 to 2007. *Spine*. 2011;36(13):1050-1058. doi:10.1097/BRS.0b013e3181e70488

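### Does labelling patients who start and stay at zero as MCID successes make the reported model performance misleading?

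*SAP*

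**What the plan says.** The SAP's Primary Endpoint Definitions dichotomise ODI, back pain and leg pain at 12 months. The general rule is that "a 30% or greater improvement in a specific score compared to baseline will be considered as achievement of MCID (clinical success"). For a patient with no symptoms on a score at the start, the same section adds: "and remained at zero for that score, this will also be defined as MCID for that score". By implication, a patient who starts at zero and has any symptoms on that score at 12 months is a failure.

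The Inclusion and Exclusion Criteria set no minimum baseline score. Under Overview, "One model will be created for each of the relevant outcomes detailed below". Under Features and Their Definitions, the baseline values of all three scores are model inputs. Under Evaluation, "Resampled training performance as well as performance on the external validation set will be assessed for discrimination and calibration", with no split by baseline value. Under Predictive Modeling, "The one final model will then be assessed on the external validation data only once".

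**The concern.** A score of zero cannot fall, and a percentage change from zero is undefined. For these patients success can only mean remaining symptom-free, and failure means new symptoms. Patients who start above zero succeed by improving. The SAP foresees zero-baseline patients, since it writes a rule for them. It then fits one model per score and reports metrics on everyone together.

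If the two groups were frequent and behaved differently, a reader of the pooled AUC could not tell how well improvement itself is predicted. Good overall calibration could hide poor calibration in the zero-baseline group. Expected Results also promises a public web tool, and a user with a zero baseline might read its output as a chance of improvement on a score that cannot improve.

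**Working it through.** **The plan's own figures.** From Sample Size: 200 / 0.20 = 1000 training patients; 300 × 0.20 = 60 minority-class patients in validation; 1000 + 300 = 1300. All three reproduce.

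**The label.** Let B be the baseline score and F the 12-month score. For B > 0, (B − F)/B ≥ 0.30 is the same as F ≤ 0.7 × B. Setting B = 0 gives F ≤ 0, so F = 0. Zero to zero is a success and zero to any positive score is a failure, as the SAP has it. The rule extends one condition to its end point. It is not a jump either: on a 0–10 NRS recorded in whole points (an assumption), a baseline of 1 needs F ≤ 0.7, hence F = 0. Patients starting at 1 and at 0 then face the same 12-month target.

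**Assumptions for size.** The documents give no zero-baseline rate. Take z = 2–15% with a zero baseline, p = 20–60% of them above zero at 12 months, and m = 20% or 40% failing among the others (the range under Sample Size).

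- Zero-baseline patients in validation: 300 × 0.02 = 6 to 300 × 0.15 = 45. Failures among them: 6 × 0.20 = 1.2 to 45 × 0.60 = 27.
- Their share of all failures is zp / (zp + (1 − z)m). At m = 20%: 0.004/0.200 = 2% to 0.090/0.260 = 35%. At m = 40%: 0.004/0.396 = 1% to 0.090/0.430 = 21%.

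**Discrimination.** Take an AUC of 0.67 in patients above zero (logistic-normal risk) and a calibrated constant prediction p for the zero group. Pooled AUC by numerical integration:

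| m | z | p = 20% | p = 40% | p = 60% |
|---|---|---|---|---|
| 20% | 2% | 0.668 | 0.673 | 0.682 |
| 20% | 15% | 0.654 | 0.685 | 0.735 |
| 40% | 2% | 0.672 | 0.668 | 0.671 |
| 40% | 15% | 0.683 | 0.654 | 0.676 |

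The shifts are −0.016 to +0.065 at m = 20% and −0.016 to +0.013 at m = 40%. The Hanley–McNeil 95% half-width at AUC 0.67 is 0.081 for 60 failures against 240 others, and 0.063 for 120 against 180. Every shift on this grid is smaller.

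If instead no zero-baseline patient develops symptoms (p = 0), the pooled AUC is [(1 − z)(1 − m) × 0.67 + z] / [(1 − z)(1 − m) + z]. At z = 15%, m = 40% this is (0.51 × 0.67 + 0.15)/0.66 = 0.745, a shift of +0.075. Failures then number 300 × 0.85 × 0.40 = 102, and the half-width is 0.066. The shift exceeds it here.

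**Calibration.** Simulate a GLM with a linear baseline term, with baselines above zero drawn from a normal (65, 20) limited to 5–100. The zero group's expected/observed ratio runs from about 0.5 to 3 while the pooled ratio is 1.00, if failure is unrelated to baseline or falls as baseline rises. Three facts limit what this shows:

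- The pooled 1.00 holds by construction, because the model is judged on the data it was fitted to. Predictive Modeling plans upsampling or SMOTE for major imbalance. Weighting the classes to 50:50, as a stand-in without recalibration, gives a pooled ratio of about 1.8–2.4 at 20% failure and 1.15–1.34 at 40%. That is not a reassuring figure hiding a subgroup.
- The extremes occur at a 2% share, about 6 validation patients. At 15% the range is about 0.8–1.7.
- The limits depend on simulation choices. If failure rises with baseline, ratios go down to about 0.25. The GLM is one of seven candidate algorithms, several can fit a nonlinear baseline effect, and selection uses calibration metrics.

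**The case for a change.** The strongest case for the concern is calibration. Evaluation itself treats calibration as central and values a sound individual probability above a yes/no prediction. A public tool is planned, and none of the listed metrics would show whether zero-baseline patients receive sound probabilities. The AUC shift is also a change in what is measured, so a larger validation set would narrow the interval without removing the shift. At p = 0 and a 15% share it exceeds the sampling interval. A count and a table with and without these patients would need no refit and no extra patients, and could use the same single set of predictions.

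Part of this stands. The label does mean staying symptom-free for this group, no separate result is planned, and a count would be informative. It does not make the plan wrong. The SAP does not forbid such a count, and the missing table changes no label, model or planned analysis. Expected Results gives no wording for the tool's output, so the feared misreading rests on text the document does not contain. With 6 patients and about one failure, observed against predicted risk would say little. Restricting each model to patients above zero would leave 1000 × 0.98 × 0.20 = 196 down to 1000 × 0.85 × 0.20 = 170 failures at 20% failure, whereas the plan states that "a minimum of 200 patients with a negative outcome (minority class) are required". The tool would then also give no prediction on that score for zero-baseline patients.

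**Conclusion.** The concern does not hold. The SAP fixes the zero-baseline case openly and in advance, in the only way that follows from a 0.7-times-baseline threshold, and nothing elsewhere contradicts it. Followed as written, the plan yields valid discrimination and calibration for the endpoint it defines, and the models receive the baseline scores needed to recognise these patients.

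The size of any effect cannot be found from the documents. On the assumed 2–15% zero-baseline share with 20–60% developing symptoms, the AUC shift is −0.016 to +0.065, inside the validation interval. At a 2% share it is at most 0.012. If none develop symptoms it can reach +0.075 at a 15% share. No success criterion depends on it: a model that is "likely to predict consistently with an AUC of at least 0.70" is listed under Expected Results as an expectation. Separate reporting of zero-baseline patients is a matter of preference.

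### The training minimum of 200 minority-class cases covers at most 20 inputs under the plan's own rule of 10 cases per input; with the seven indications coded separately there are at least 25 inputs and at most 8.0 cases per input

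*SAP*

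**What the plan says.** The Sample Size section of the SAP gives two rules of thumb. The first concerns the number of inputs: "Roughly, it can be said that a bare minimum of 10 positive cases are required per included input variable". It is illustrated by an example: "a prediction based on 10 input features for an outcome occurring in only 10% of cases would require at least 1000 patients". The section warns that models behave erratically below this level and that "high variance in performance among splits is observed when sample sizes are smaller than calculated with this rule of thumb". The second rule is a floor that does not depend on the number of inputs: "we do not recommend developing ML models on cohorts with less than 100 positive cases".

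The section then sets this study's size. On incidence it says "For sample size calculation, we take 20% for a conservative estimate", the low end of a quoted range of 20% to 40%. On the number of cases, "based on our expertise and on the rules of thumb mentioned above", it concludes: "we estimate that a minimum of 200 patients with a negative outcome (minority class) are required to extract generalizable feature relationships". That leads to about 1000 patients for training, 300 for external validation and 1300 in total.

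Features and Their Definitions lists 19 top-level inputs. Three of them allow several answers per patient: indications (seven items), index levels (T12 to S1) and surgical approach (four items). Two more have over two categories: smoking (three) and race/ethnicity (four). Predictive Modeling says that the data will be one-hot-encoded, that every feature goes into the model at the start, and that recursive feature elimination (RFE) is used only if needed. It also says: "Features or patients with a missingness greater than 25% will be excluded".

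**The concern.** The SAP cites a cases-per-input rule as part of the basis for 200 cases, but never says how many inputs those cases are meant to serve, or whether an input is a listed feature or an encoded column. The answer decides whether the rule is met. The list fits within 200 cases only when it is counted by bullet, and one bullet holds seven separate yes/no facts that can occur together.

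At stake is the claim that 1300 patients are the minimum for a robust model. The SAP itself describes what to expect below the rule: erratic models and performance that varies between splits. A reader who takes the cited rule as support for the minimum would be reassured by a check that the planned coding does not pass.

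**Working it through.** **Inputs from the SAP.** Rule: 10 cases per input. Incidence: 20%. Training cases: 200. Training patients: 1000. Validation patients: 300. Top-level features: 19. The rule is applied to the minority class, as the plan's own calculation does.

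**The plan's figures reproduce.**
- Training: 200 / 0.20 = 1000.
- Total: 1000 + 300 = 1300.
- Worked example: 10 features × 10 = 100 cases; 100 / 0.10 = 1000.

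**Capacity of 200 cases under the rule.** 200 / 10 = 20 inputs at most.

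**Counting the inputs.**
- One input per bullet: 19, needing 19 × 10 = 190 cases.
- Only the seven indications separated: 19 − 1 + 7 = 25. This needs no assumption about the other features, and is a lower bound once the indications are separated, because four further multi-level features still count as one each.
- The same without height and weight, which BMI makes redundant: 25 − 2 = 23.
- All multi-level features expanded, two-level features kept as one column: 14 single inputs + 7 indications + 6 index segments + 2 smoking + 3 race + 4 approach = 36 (reference coding for smoking and race).
- All categories of smoking and race kept: 14 + 7 + 6 + 3 + 4 + 4 = 38. With T12 to S1 counted as seven vertebrae instead of six segments: 39.

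The SAP fixes neither six versus seven levels, nor reference versus full coding, nor whether index levels and approach are expanded. The range 36 to 39 therefore rests on assumptions.

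**Cases per input (200 / inputs) and break-even incidence (inputs × 10 / 1000).**

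| Counting | Inputs | Cases per input | Rule of 10 | Incidence from which 1000 patients meet the rule |
|---|---|---|---|---|
| One per bullet | 19 | 10.5 | met | 19% |
| Limit of the rule | 20 | 10.0 | met | 20% |
| Indications separated, no height or weight | 23 | 8.7 | not met | 23% |
| Indications separated | 25 | 8.0 | not met | 25% |
| All multi-level features expanded, low | 36 | 5.6 | not met | 36% |
| All multi-level features expanded, high | 39 | 5.1 | not met | 39% |

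**Can the plan's other steps close the gap?** To get from 25 inputs to 20, RFE or the 25% missingness exclusion would have to remove at least five. RFE is conditional and has no target number, and the plan assumes no loss of features through missingness. Random upsampling or SMOTE adds no independent cases.

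**The case against.** The best defence is that the SAP counts features, not columns. Its worked example speaks of input features, the feature list uses the same term, and that list has 19 entries needing 190 cases. This probably explains where 200 came from, and no sentence ties the rule to encoded columns. It still requires seven non-exclusive indications to count as one variable, which does not fit one-hot encoding with every feature supplied to the model.

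Other parts of the defence stand:
- The limit is 20 inputs, not 19. Expanding smoking alone to two columns gives 20 and still meets the rule.
- The rule is called rough, and the sponsor's expertise is a second stated basis for the 200.
- The separate floor of 100 cases is met twice over.
- 20% is the low end of the range. At 30%, 1000 patients give 300 cases, or 12.0 per input for 25 inputs, though still 8.3 to 7.7 for 36 to 39. At 40% they give 400 cases, or 11.1 to 10.3 for 36 to 39.
- The sizes are minima, and the SAP expects more data to help.

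A reader might infer that enrolment must rise, for example to 250 / 0.20 = 1250 training patients and 1550 in total for 25 inputs. The documents do not support that as a requirement: the rule is not the only basis for the 200, and 25 is a lower bound under separate coding, not a count that the SAP has fixed.

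**Conclusion.** The point holds in a limited form. At the plan's own 20%, 200 cases meet its rule only for 20 inputs or fewer. With the indications coded separately there are at least 25 inputs and at most 8.0 cases per input (8.7 if height and weight are dropped). With every multi-level feature expanded, under the assumptions above, there are 5.6 to 5.1. The 25-input figure needs only that the indications enter as separate variables and that no features are removed first.

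The calculation of 1000 and 1300 is correct. The defect is that the number of inputs is not stated and that the minimum falls short of a rule cited in its support. A reader might go further and infer that the final models will be unstable or the final dataset too small. The documents do not show this: incidence may be higher, more patients may be contributed, and fewer inputs may remain. Nor does the rule require a hard cap of 20 inputs. The point is minor to should-fix.

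**What to change.** In the Sample Size section, state the number of encoded candidate inputs and that the rule of 10 applies to them. Keep 1000 + 300, but restate its adequacy, for example:

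*200 minority-class cases give at most 8.0 cases per input for at least 25 inputs (about 5 to 6 if all multi-level features are expanded), below the rule of 10; the minimum rests on our expertise and on the floor of 100 cases.*

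Once the coding is settled, replace these bounds with the actual count and ratio. Optionally, drop redundant inputs, such as height and weight given BMI, without looking at outcomes.

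The cost is SAP wording only: no extra patients and no forced loss of inputs. The downside is that the stated adequacy of the minimum becomes less favourable.
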